- b. Subjects who have 17p deletion or TP53 mutation as assessed by local laboratory (in bone marrow or peripheral blood) may be considered for enrollment. A recent test is desirable but any previous positive test is acceptable. Subjects that do not have the 17p deletion or TP53 mutation or have an unknown status are also eligible.
- c. For females of childbearing potential, as defined in the protocol, a urine pregnancy test must be obtained and processed locally at Week 1 Day 1, if it has been > 7 days since obtaining the serum pregnancy results at Screening. During the study, a urine pregnancy test can be performed at the discretion of the investigator or per local guidelines.
- d. All protocol-related serious adverse events and nonserious adverse events must be collected from the signing of the study-specific informed consent until study drug administration.
- e. A complete physical examination will be performed at Screening. A symptom directed physical examination may be performed as needed. Refer to Section 5.3.1.1 Physical Examination, for more details.
- f. For subjects who have a dose interruption lasting more than 1 week during the first 5 weeks of dose-titration or more than 2 weeks when at the daily dose of 400 mg, the TLS risk should be reassessed to determine if restarting at a reduced dose is necessary.
- g. All clinical laboratory tests will be analyzed by the local laboratory. Required tests are listed in Table 4 Clinical Laboratory Tests, refer to Section 5.3.1.1 Study Procedures, sub header Hematology and Chemistry as well as Section 6.1.9 Toxicity Management, for more details.
- h. For all subjects, if the screening labs were done more than 72 hours before the planned first dose, the chemistry/hematology panel should be repeated and results reviewed prior to the initial dose in order to make a treatment decision. Labs should be assessed and pre-existing abnormalities should be corrected.
- i. For all subjects, on the day of Week 1 Day 1, before dosing, the chemistry/hematology panel should be collected. The results of the labs drawn on Week 1 Day 1 need to be reviewed prior to dosing **IF** an additional lab within 72 hours of the initial dose at Week 1 Day 1 was not drawn **AND** reviewed.
- j. For all subjects, the chemistry/hematology panel should be monitored at 6 to 8 hours and at 24 hours after the first dose of venetoclax (20 mg) and after the first dose increase (50 mg). The next venetoclax doses should not be administered until the 24 hour lab results have been evaluated. Electrolyte abnormalities should be corrected promptly.
Note: There is a ± 2 hour window around the 24 hour lab draw.
- k. For all subjects, within 72 hours of each subsequent dose increase, the chemistry/hematology panel should be repeated. The results should be reviewed prior to dose increasing.
- l. Prior to dosing, on the day of each subsequent dose increase, the chemistry/hematology panel is required. The results of the labs drawn on Day 1 of each dose increase need to be reviewed prior to dosing **IF** additional labs within 72 hours of the dose increase were not drawn **AND** reviewed.
- m. For subjects who continue to be at risk of TLS, the same lab monitoring schedule of 6 to 8 hour and 24-hr post dose should be followed at the subsequent dose increases.
Note: There is a ± 2 hour window around the 24 hour lab draw.
- n. All measurable disease must be documented at Screening by laboratory testing, physical examination and CT scans (or MRI if CT is medically contraindicated); bone marrow examinations are not required at screening but results will be recorded if available. All baseline evaluations should be performed as closely as possible to the beginning of treatment. For all subsequent disease assessments, disease response will be assessed by the investigator based on the analysis of clinical laboratory tests (hematology) and a complete physical examination at Week 24, Week 36 and Week 48.

- o. CT scans with contrast (or MRI if CT is medically contraindicated) should include neck, chest, abdomen and pelvic sequences can be accepted if previously performed within 35 days prior to the initial venetoclax dose. Otherwise, CT scans (or MRI) must be performed within the 28 day screening period. To confirm response, a CT scan (or MRI) must be performed at Week 48 for all subjects. CT scans (or MRI) may be performed 7 days prior to the scheduled Week 48 visit. If a subject exhibits clinical signs of possible disease progression (i.e., increased or de novo enlargement of liver, spleen or lymph nodes on physical examination) without an increase in lymphocytes meeting the progression of disease criteria, then additional assessments including contrast-enhanced CT scan and/or bone marrow can be performed to confirm or rule out disease progression. Refer to Section 5.3.1.1 Disease Assessments and Computed Tomography Scans, for more details. For patients with only Partial Remission at Week 48, an additional CT and a bone marrow examination can be done between Week 48 and Week 108 to confirm CR if there is a possibility that a patient is in Complete Remission based on laboratory tests and a disease assessment physical exam.
- p. For determination of complete remission (CR), the CT scan and bone marrow are required to be negative, per the IWCLL NCI-WG guidelines. If the subject achieves a CR by clinical criteria and confirmatory CT scan, a bone marrow aspirate and biopsy will be performed to confirm the CR. Refer to Section 5.3.1.1 Disease Assessments and Bone Marrow Aspirate and Biopsy, for more details.
- q. Venetoclax tablets should be taken orally once daily with a meal and water in the morning at approximately the same time each day. Dosing should occur at study visits on Week 1 Days 1 & 2 through Week 5 Days 1 & 2.
- r. The Quality of Life Questionnaires should be administered and completed prior to any other study procedures being performed at these visits. Refer to Section 5.3.1.1, Quality of Life Assessments for further information.
- s. 30-Day Safety Follow-up visit should occur approximately 30 days (\pm 3 days) after the last dose of venetoclax.
- t. Upon discontinuation of study drug treatment, survival information (i.e., the date/cause of death, post treatment cancer therapies, etc.) will be collected every 6 months (\pm 7days) for a period of 2 years.
- u. ECOG performance status may be performed within 72 hours before or after the scheduled visit starting with Week 24.
- v. Survival information includes i.e., the date/cause of death, post treatment cancer therapies, etc.
- w. In countries where venetoclax is not commercially available, subjects who continue to derive benefit after 2 years of treatment may be able to extend their treatment for up to 2 additional years. AbbVie will work with the investigator on a case by case basis to consider the potential continuation of venetoclax therapy. Subjects who participate in the 2 year Extended Access phase will have study drug assigned at Week 108. For patients that are not participating in the 2 year Extended Access phase the Week 108 visit is the Final visit. The specific study assessments to be performed at the Extended Access visits are detailed in [Appendix E](#), Study Activities.

Appendix E. Schedule of Extended Access Phase*

Add: new appendix title and text

Appendix E. Schedule of Extended Access Phase*

Procedure	W108 D1	W120 D1	W132 D1	W144 D1	W156 D1	W168 D1	W180 D1	W192 D1	W204 D1	W216/ Final Visit	30 Day Safety Visit^d	Post Treatment Follow up^e
Vital signs**	X									X	X	
Physical Examination ^{a**}	X									X	X	
ECOG Performance Status**	X									X	X	
Hematology/Chemistry***	X									X	X	
Adverse Event/Concomitant Medication Assessment	X	X	X	X	X	X	X	X	X	X	X	X
Venetoclax dispensation and accountability****	X	X	X	X	X	X	X	X	X			
Collection of Survival Information ^b	X	X	X	X	X	X	X	X	X	X	X	X
Quality of Life Questionnaires (EORTC QLQ-30, EORTC QLQ-CLL16, EQ-5D-5L) ^c	X											

* In countries where venetoclax is not commercially available, subjects who continue to derive benefit after 2 years of treatment may be able to extend their treatment for up to 2 additional years. AbbVie will work with the investigator on a case by case basis to consider the potential continuation of venetoclax therapy.

** Within 72 hours before or after scheduled visit.

*** Within 72 hours prior to scheduled visit.

**** The visit window for scheduled visits is \pm 2 days.

- a. Refer to Section [5.3.1.1](#) Physical Examination, for more details.
- b. Survival information includes i.e., the date/cause of death, post treatment cancer therapies, etc.
- c. The Quality of Life Questionnaires should be administered and completed prior to any other study procedures being performed at these visits. Refer to Section [5.3.2.2.1](#) Health Economic and Patient-Reported Outcome Measures, for further information.
- d. 30-Day Safety Follow-up visit should occur approximately 30 days (\pm 3 days) after the last dose of venetoclax.
- e. Upon discontinuation of study drug treatment, survival information (i.e., the date/cause of death, post treatment cancer therapies, etc.) will be collected every 6 months (\pm 7 days) for a period of 2 years

3.0 Introduction

This statistical analysis plan (SAP) describes the full statistical analyses for venetoclax (ABT-199) Protocol M15-889. Study M15-889 evaluates the quality of life of subjects with relapsed or refractory chronic lymphocytic leukemia (CLL). Quality of life is assessed based on patient-reported outcome (PRO) measures, including the European Organization for Research and Treatment of Cancer Quality of Life Core Questionnaire (EORTC QLQ-C30), the European Organization for Research and Treatment of Cancer Quality of Life Questionnaire Chronic Lymphocytic Leukemia Module (EORTC QLQ-CLL16), and the EuroQoL 5 Dimension 5 Level Questionnaire (EQ-5D-5L).

This statistical analysis plan (SAP) provides details to elaborate the statistical methods outlined in Study Protocol M15-889 Amendment 1 dated 11 July 2016 and Amendment 2 dated 30 January 2018. It will provide details of statistical methods and describe analysis conventions to guide the statistical programming work.

Unless noted otherwise, all analyses will be performed using SAS[®] version 9.3 or newer (SAS Institute Inc., Cary, NC USA).

The SAP will not be updated in case of future administrative or minor amendments to the protocol unless the changes have any impact on the analysis of the study data.

4.0 Study Objectives, Design and Procedures

4.1 Objectives

Primary Objective

The primary objective of this study is to evaluate the impact of venetoclax monotherapy on the quality of life of subjects with relapsed or refractory chronic lymphocytic leukemia (CLL). Quality of life will be assessed by the Global Health Status/Quality of Life (GHS/QoL) subscale of the EORTC QLQ-C30.

Secondary Objectives

The secondary objectives are to

- evaluate the impact of venetoclax monotherapy on quality of life based on the EORTC QLQ-CLL16, EQ-5D-5L, and the remaining subscales from the EORTC QLQ-C30
- complete remission rate (CR + CRi)
- overall response rate (ORR)
- duration of overall response (DOR)
- time to progression (TTP)
- duration of progression-free survival (PFS)
- overall survival (OS)
- complete remission rate (CR + CRi) in BCRi treated subjects

The safety and tolerability of venetoclax in subjects with relapsed/refractory CLL will also be evaluated.

4.2 Study Design and Plan

This is an open-label, single arm, Phase 3b, multi-center study evaluating the impact of venetoclax monotherapy on the quality of life in relapsed/refractory CLL.

This study is designed to enroll approximately 200 subjects to meet scientific objectives without enrolling an undue number of subjects in alignment with ethical considerations.

Subjects meeting the eligibility criteria will be treated with venetoclax once daily (QD), continuously up to 2 years provided they continue to tolerate the drug, have no evidence of disease progression (based on Investigator's assessment), do not have unacceptable toxicity, and do not meet any of the protocol specified criteria for discontinuation.

Dosing Schedule Overview

Venetoclax is administered orally once daily (QD), continuously. To mitigate the risk for tumor lysis syndrome (TLS), a lead-in period (up to 5 weeks) is employed to evaluate a step wise dose-titration as specified in the protocol, and [Figure 1](#).

Figure 1. 5-Week Dose-Titration Schedule

Week	VENETOCLAX Daily Dose
1	20 mg
2	50 mg
3	100 mg
4	200 mg
5 and beyond	400 mg

4.3 Sample Size

An improvement in the EORTC QLQ-C30 GHS/QoL subscale of 5 units is considered to be a clinically meaningful difference to subjects. From a prior study of venetoclax monotherapy in 17p del R/R CLL subjects (Study M13-982), the standard deviation was approximately 20.5 for the GHS/QoL subscale. Using a one-sided alpha of 0.025, 90% power, and a standard deviation of 20.5; 177 subjects are required to reject the null hypothesis in favor of the alternative hypothesis that venetoclax improves GHS/QoL by at least 5 units. To account for potential drop-outs at Week 48, a total of 200 subjects to be dosed.

4.4 Interim Analysis

Data Monitoring Committee (DMC)

A Data Monitoring Committee (DMC) has been independently organized to support the review of safety data associated with venetoclax monotherapy dosing. The DMC will

review the safety data with an initial review to occur when approximately 20 subjects have completed a minimum of 12 weeks of treatment.

A separate charter will be created to provide detailed descriptions of the schedule of analyses and the DMC meetings. DMC membership, responsibilities and the description of the data coordinating center are documented in the charter.

4.5 Timing of Quality of life and Efficacy Analyses and Safety Evaluations

Table 1. Summary of Analyses with Cutoff Dates and Data Included

Reason	Database Version	Cutoff Date	QoL/Efficacy Data Included	Safety Data Included
DMC	A	24 Apr 2017	Not included	All safety data ^a
DMC	F	03 Nov 2017	Not included	All safety data ^a
DMC	G	30 Apr 2018	Included	All safety data ^a

a. Safety population is defined in Section 5.1.1.

Quality of life, efficacy, and safety analysis occur when all subjects participating in the study have completed the 48-week disease assessment or have discontinued venetoclax (including early termination of the study). Quality of life, efficacy, and safety data up to the cutoff date specified in Table 1 will be considered. During this data collection period, active subjects continue to receive venetoclax, as applicable. When data collection is complete and all data management quality assurance (QA) and quality control (QC) procedures are performed, the clinical database data should be extracted for documentation and statistical analyses. The study will be considered completed when the last enrolled subject discontinues or completes the dosing regimen.

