8.1.3 Timing of Study Endpoints and Safety Evaluations

The date the last enrolled subject has completed their Week 48 quality of life and disease assessments, or after all enrolled subjects have discontinued venetoclax, whichever is earlier, will be defined as the data "cutoff" date for the analyses. Quality of life, efficacy and safety data up to and including this date will be collected. Exact data cutoff date for the analysis will be detailed in the SAP which will be signed off prior to the data cut-off date. During this data collection period, active subjects will continue to receive venetoclax, as applicable. When data collection is complete and all data management quality assurance (QA) and quality control (QC) procedures are performed, the clinical database data will be extracted for documentation and statistical analyses. Any active subjects will continue to receive venetoclax until they discontinue or for up to 2 years. Once the last enrolled subject discontinues/completes the study, the study will be considered complete and all remaining data will be collected and entered into the clinical database.

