13.0 Completion of the Study

The investigator will conduct the study in compliance with the protocol and complete the study within the timeframe specified in the contract between the investigator and AbbVie. Continuation of this study beyond this date must be mutually agreed upon in writing by both the investigator and AbbVie. The investigator will provide a final report to the IEC/IRB following conclusion of the study, and will forward a copy of this report to AbbVie or their representative.

The investigator must submit, maintain and archive any records related to the study according to ICH GCP and all other applicable regulatory requirements. If the investigator is not able to retain the records, he/she must notify AbbVie to arrange alternative archiving options.

AbbVie will select the signatory investigator from the investigators who participate in the study. Selection criteria for this investigator will include level of participation as well as significant knowledge of the clinical research, investigational drug and study protocol. The signatory investigator for the study will review and sign the final study report in accordance with the European Agency for the Evaluation of Medicinal Products (EMA) Guidance on Investigator's Signature for Study Reports.

The end-of-study is defined as the date of the last subject's last visit or date of the last follow up contact, whichever is later.

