6.4 Missing Data Imputation

Subjects with missing disease progression date, missing death date, or missing last known alive date will be considered as censored subjects for time to progression, progression free survival analysis, and survival analysis. And the subject will be censored at the interim data cutoff date.

If a respondent answers at least 50% of the items in quality of life measures, the missing items will be imputed with the average score of the answered items in the same scale. In cases where the respondent did not answer at least 50% of the items, the score for that domain will be considered missing.

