10.2 Quality of Life and Efficacy Analyses

Data collected at any point prior to the specified interim cutoff date during the study will be used in the analyses, unless otherwise specified. The population of these analyses is defined in Subsection [5.1.1](#).

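### SAP 4.5 sets a Week 48 trigger but limits the data to a DMC cut of 30 Apr 2018, a date that cannot support the SAP's own later outputs

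*SAP*

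**What the plan says.** **Protocol cutoff.** Protocol 8.1.3 defines the cutoff by an event: "The date the last enrolled subject has completed their Week 48 quality of life and disease assessments", or the point at which all enrolled subjects have stopped venetoclax, if that comes earlier. Data up to and including that date count, and the SAP is to supply the exact date.

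**SAP cutoff.** Table 1 in SAP 4.5 lists 24 Apr 2017, 03 Nov 2017 and 30 Apr 2018. Each row has DMC as its reason, and only the last includes quality-of-life and efficacy data. No row is labelled primary, Week 48 or final. The text under the table first places the analysis at the point where every participant has had the 48-week disease assessment or has discontinued. It then says: "Quality of life, efficacy, and safety data up to the cutoff date specified in Table 1 will be considered".

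**Interim wording elsewhere.** SAP 10.2 states: "Data collected at any point prior to the specified interim cutoff date during the study will be used in the analyses". SAP 6.4, on subjects with missing progression, death or last-alive dates, states: "And the subject will be censored at the interim data cutoff date". The definitions of DOR, TTP, PFS and OS in SAP 10.1.2 also censor at an interim cutoff. SAP 4.4, the section on interim analysis, describes only safety review by the DMC.

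**End of study.** SAP 4.5: "The study will be considered completed when the last enrolled subject discontinues or completes the dosing regimen". Protocol 13.0: "The end-of-study is defined as the date of the last subject's last visit or date of the last follow up contact", whichever is later. Protocol 5.1 and 5.4.1 provide for 2 years of follow-up after venetoclax stops.

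**Planned outputs.** SAP 3.0 presents the document as covering the full analyses. SAP 10.2.1 and 10.2.2 plan quality-of-life summaries out to Week 108/Final visit.

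**The concern.** A programmer needs one date for each analysis. The SAP offers a Week 48 event with no date, and a date with no stated link to that event. The only date available for quality of life and efficacy belongs to a DMC review, and three other sections call the cutoff *interim* when no interim efficacy analysis is described.

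Three things are at stake:

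- the later quality-of-life visits, which the SAP promises to summarise;
- the length of follow-up behind TTP, PFS, OS and DOR;
- possibly the number of subjects with a Week 48 value for the primary endpoint.

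The trial is also open-label and single-arm. A cutoff that is not fixed in advance leaves room to choose the date after the data have been seen.

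**Working it through.** **Inputs.** The cutoff of 30 Apr 2018 is from SAP Table 1. The first dose is Rx Day 1 (SAP 6.2). From SAP Table 2, Week 48 is nominal Day 330 with its window opening on Day 322, and the Week 108 window opens on Day 742. The original protocol is dated 04 May 2016 (Protocol 1.1). The design inputs are in SAP 4.3: "An improvement in the EORTC QLQ-C30 GHS/QoL subscale of 5 units is considered to be a clinically meaningful difference to subjects" and "Using a one-sided alpha of 0.025, 90% power, and a standard deviation of 20.5; 177 subjects are required".

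**1. The plan's own sample size.** For a one-sample mean change, n = (SD × (z₀.₉₇₅ + z₀.₉₀) / δ)² = (20.5 × 3.2415 / 5)² = 176.6, which rounds up to 177. This reproduces the plan. With 200 dosed, the implied allowance for drop-out is 1 − 177/200 = 11.5%.

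**2. Latest first dose that reaches each visit by 30 Apr 2018.** Latest first dose = cutoff − (Rx day − 1).

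| Visit | Rx day | Days subtracted | Latest first dose |
|---|---|---|---|
| Week 48, window opens | 322 | 321 | 13 Jun 2017 |
| Week 48, nominal | 330 | 329 | 5 Jun 2017 |
| Week 108, window opens | 742 | 741 | 19 Apr 2016 |

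The Week 108 date falls before the original protocol existed. A subject dosed on 04 May 2016 itself would be at Rx Day 727 on 30 Apr 2018, short of 742. No subject could therefore have an in-window Week 108 questionnaire at that cut. The combined Week 108/Final visit row could be filled only by final observations from subjects who stopped early.

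**3. Time-to-event endpoints.** The same Day 727 limit means that nobody could have reached Week 108 on treatment by the cut. For subjects who go on to complete treatment, the whole 2-year post-treatment follow-up lies after 30 Apr 2018, so it would be outside TTP, PFS, OS and DOR.

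**4. Week 48 and accrual.** The documents give no enrolment dates or counts. One indirect clue is that SAP 4.4 places the first DMC review when about 20 subjects have 12 weeks of treatment. If the 24 Apr 2017 cut was that review (an assumption), those subjects had started by 30 Jan 2017 (24 Apr 2017 minus 84 days). From then to 5 Jun 2017 is 126 days, or 18 weeks. For 30 Apr 2018 to be the Week 48 cutoff, nearly all of the other 180 or so, apart from any who had discontinued by the cut, would have had to start within those 18 weeks. That is possible, but the documents do not show it.

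**5. What a shortfall would cost.** Take δ = 5, SD = 20.5 and one-sided 0.025. Normal-approximation power is Φ(δ√n/SD − 1.96). The t-test version uses the noncentral t distribution with noncentrality δ√n/SD. The 95% CI half-width is 1.96 × SD/√n.

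| Evaluable at Week 48 | Power, t-test | Power, normal | CI half-width |
|---|---|---|---|
| 177 (planned) | 90% | 90% | 3.02 |
| 150 (assumed) | 84% | 85% | 3.28 |
| 100 (assumed) | 68% | 68% | 4.02 |

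If every subject had reached Week 48 or discontinued by 30 Apr 2018, the primary endpoint would lose nothing.

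**The case against.** The sponsor has a good reply on several points.

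- **The SAP does state a Week 48 trigger.** It comes in the sentence before the data limit and is close to Protocol 8.1.3, which also asks the SAP for a calendar date. A reader might infer that the SAP overrides the protocol's Week 48 cutoff. The text does not support that: it contains both rules and fails to reconcile them.
- **Loss of Week 48 data is not shown.** A reader might infer that subjects drop out of the primary endpoint. That requires applying one sentence of SAP 4.5 and ignoring its neighbour, and it requires accrual dates that the documents lack. Subjects who have discontinued satisfy the trigger whatever their start date.
- **Post-treatment deaths are not ignored.** SAP 10.1.2 counts deaths after discontinuation and uses last contact dates and the survival form. Post-treatment follow-up before the cutoff enters OS, and only what comes later is excluded.
- **One cutoff for efficacy follows the protocol.** Protocol 8.1.3 applies a single cutoff to quality of life, efficacy and safety, and says that remaining data will be collected without naming a later analysis. A final-analysis row is therefore an addition and does not restore a protocol commitment.
- **The completion sentence changes no estimate alone.** No SAP endpoint or censoring rule refers to study completion.

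All five replies stand. They do not answer the Week 108 arithmetic, which needs no accrual data, or the absence of any row for the analyses that the SAP itself plans.

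**Conclusion.** The point holds as an internal contradiction in SAP 4.5, carried into Sections 6.4, 10.1.2 and 10.2. Two consequences rest only on dates in the documents. A 30 Apr 2018 cut leaves no in-window Week 108 questionnaires, and it excludes later progression and survival follow-up from TTP, PFS, OS and DOR.

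The effect on the primary endpoint cannot be determined. It ranges from none to a material loss of power, and the 150 and 100 in the table are illustrations, not estimates. They also take the plan's SD of 20.5 as correct.

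The completion sentence conflicts with Protocol 13.0 and should be corrected for consistency. The sample size of 177 is not in question.

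**What to change.** 1. Add a primary analysis row to SAP Table 1, defined by the Protocol 8.1.3 event: the last enrolled subject's Week 48 quality-of-life and disease assessments, or all subjects discontinued, whichever is earlier. The current SAP trigger names only the disease assessment. Enter the calendar date when it is known.
2. Add a final analysis row at the Protocol 13.0 end of study, covering OS, PFS, TTP, DOR and the later quality-of-life visits.
3. In SAP 6.4, 10.1.2 and 10.2, replace the interim cutoff with the primary or final analysis cutoff as applicable. Use the protocol's inclusive rule throughout, because SAP 4.5 takes data up to the cutoff and SAP 10.2 takes data before it.
4. Keep the DMC rows for safety review only, or state what the quality-of-life and efficacy data in the 30 Apr 2018 row are for.
5. Align the study-completion sentence in SAP 4.5 with Protocol 13.0.

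The cost is SAP wording and one rerun of the affected tables at end of study. No new data are needed, since the protocol already collects the follow-up.
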